## Introduction

Musculoskeletal disorders (MSD) is a widespread public health issue that adversely affects a person's functioning, quality of life, and health. It is one of the main reasons people live with disabilities for a long time worldwide. (Nogueira et al., 2023)

Monks are those who practice religious asceticism through monastic living, i.e., those who were celibate (not married) and constantly residing in a monastery. They pray for five to ten hours at churches. Orthodox monks work long hours and have little free time while living in monasteries. (Avdeenko, et al., 2019)

Radical Christian lifestyle takes the shape of monasticism. It has a title and a structure for Christian life that will direct how homes and communities are built. The monasteries evolved into hubs of Christian activity. They were at the vanguard of mission, academic institutions, private and public places of prayer. sharing financial resources with neighbours and the less fortunate. (Binns,2021).

The Coptic monk's day begins at sunrise. After sleeping for the first half of the night, the monk's day officially starts at midnight. starting with the service of the midnight psalmody and accompanying prayer, then continuing with scripture readings till dawn. If the Divine Liturgy is held, he is welcome to attend. He starts working at the specific job that has been given to him and for which he is qualified. Depending on the time of day, he is also expected to be silently praying or participating in other prayers. He then starts one of the numerous tasks at the monastery. (Sadek, 2012).

Vivian, (2001) said that "prayer became explicit and more fervent when the monk interrupted his work and stood up, often lifting his arms to heaven after Ving knelt and prostrated himself on the ground. The frequency of this prayer depend on individual and circumstance, so the worship of God in prayer, used to bend his knees a hundred times a night and as many times a day ". Therefore, the monk is always prostrating in his day.

Prostration from a standing to a kneeling position, the exercise is performed by placing the head down and hitting the ground with the forehead, keeping the palms parallel to the ears, and flexing the elbows for a brief period of time. (Nazish, & Kalra, 2018).

The primary function of monks and nuns in monastic stories is performing religious duties. After that, they engage in labor-intensive tasks like farming, raising crops, making candles, iconography, and other handicrafts, as well as producing goods that can be sold for use in homes or in churches, such as incense and rosaries. food and drink products made in the monastery. (Christos, 2017)

Orthodox Christian lifestyle is beneficial for maintaining mental health, but not for maintaining physical health. Low back pain/sciatica, chronic venous insufficiency (caused by prolonged standing), and periarticular/soft tissue rheumatic illnesses (tendinitis, bursitis/fasciitis, enthesitis, etc.) are the most common diseases. This conclusion is supported by the fact that repetitive physical stress from manual and technical work, along with prolonged standing while praying in church, may trigger the start of the aforementioned health issues. An earlier study that looked at impairment among monks found that the rates of activities of daily living connected to disability were much higher than those of the general population. More frequently than the general population, monks reported a number of chronic illnesses, bodily ailments, and issues with daily tasks. (Merakou, et al., 2017)

This study determined the pattern of musculoskeletal disorders among monks and nuns in different monasteries in Egypt .

## **Statement of the problem**

This study aims to answer the following questions:

What is the correlation between monastic years, gender and musculoskeletal disorders?

## Hypotheses

This study will be hypothesized that:

- 1- There is no correlation between years of monastic and musculoskeletal disorders among Egyptian monks.
- 2- There is no correlation between musculoskeletal disorders and gender of monks and nuns.

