## Purpose of the study

This study will be conducted to:

- 1- Survey the relationship between duration of years since ordination and musculoskeletal disorders among Egyptian monks.
- 2- Survey the relationship between musculoskeletal disorders and gender of monks and nuns.

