#### **Delimitations**

This study will be delimited to:

- 1- Sample size will be 400.
- 2- Age starts from 24 years old and more.
- 3- Body mass index (BMI) between 18.5 to 24.9 kg/m2
- 4- Years of ordination
  - (1-3) years "novice" or "probationary".
  - (4-10) years of monasticism.
  - more than 10 years of monasticism.
- 5- Samples will be selected from several monasteries in Egypt.
- 6- All data collected by Arabic version of Nordic questionnaire.

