# **Chapter 3**

# Subjects, Materials and Methods

This study will be conducted at several monasteries in Egypt to make correlation between musculoskeletal disorders and monastic years among monks and nuns.

**Study design:** Observation study - cross-sectional survey.

**Participants:** sample size of monks will be 400 subjects of both genders (monks and nuns) randomly selected from different monasteries, Participants aged from 24 years old and above thought monastic years. As:

- (1-3) years "novice" or "probationary"
- (4-10) years of monasticism
- more than 10 years of monasticism

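### The years-of-ordination analysis pools monks and nuns but names no gender term, and the wording of Hypothesis 1 and Purpose 1 should match the Methods

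*SAP*

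**What the plan says.** The SAP states the question about years and MSD in several places.

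- **Hypotheses, item 1:** "There is no correlation between years of monastic and musculoskeletal disorders among Egyptian monks". Item 2, directly below, reads "There is no correlation between musculoskeletal disorders and gender of monks and nuns".
- **Purpose of the study, item 1:** "Survey the relationship between duration of years since ordination and musculoskeletal disorders among Egyptian monks". Item 2 again names monks and nuns.
- **Statement of the problem:** "What is the correlation between monastic years, gender and musculoskeletal disorders". It takes years and gender together and names no population.
- **Subjects, Materials and Methods:** the study is conducted "to make correlation between musculoskeletal disorders and monastic years among monks and nuns". The participants sentence in the same section begins "sample size of monks will be 400 subjects of both genders (monks and nuns".
- **Inclusion criteria:** both genders are eligible.
- **Statistical Analysis:** a Pearson chi-square and logistic regression relate MSD prevalence to years of ordination, at a 0.05 level. No population restriction, gender term or other covariate is named.

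The section on the association between sex and MSDs reports higher prevalence in females. Gender is recorded in section A of the questionnaire and by separate monk and nun boxes on the form in Appendix II.

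**The concern.** There are two issues, of unequal weight.

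The lesser one is wording. Hypothesis 1 and Purpose 1 speak of monks, while the items beside them and the Methods speak of monks and nuns. Read alone, they permit a test in men only.

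The weightier one arises under the reading that the Methods support, in which both genders are analysed together. The Statistical Analysis section then tests years of ordination in a mixed group and does not say that gender enters the model. By the SAP's own review, gender is related to the outcome. If it is also related to the ordination band, because nuns make up more of one band than of another, the crude comparison of bands mixes a gender difference into the years result. It could show a years effect where there is none, or hide one that exists, depending on the direction of the imbalance.

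**Working it through.** **Population and size.** The only sample size is 400. The Delimitations give it as "Sample size will be 400", and the Methods give it for both genders. The SAP shows no calculation behind 400 and no gender split, so there is no derivation to reproduce. No men-only analysis set is defined anywhere.

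**Inputs for the pooled analysis**

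- From the SAP: three ordination bands (1-3, 4-10 and more than 10 years), N = 400, and higher MSD prevalence in females (direction only).
- Assumed, because the SAP does not give them: the share of nuns in each band and MSD prevalence by gender.

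**Formula.** Suppose years of ordination have no effect, so that each gender has the same prevalence in every band. Crude prevalence in a band is (nun share × nun prevalence) + (monk share × monk prevalence). The difference between two bands is then

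spurious difference = (difference in nun share) × (nun prevalence − monk prevalence).

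**Worked case.** Assume nuns at 65%, monks at 50%, and nuns forming 30% of novices and 60% of the band above 10 years.

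- Novices: 0.30 × 65 + 0.70 × 50 = 54.5%
- More than 10 years: 0.60 × 65 + 0.40 × 50 = 59.0%
- Difference: 4.5 points, which equals 0.30 × 15
- Crude odds ratio: (59.0/41.0) / (54.5/45.5) = 1.439/1.198 = 1.20, where the true value within each gender is 1

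**Range of the spurious difference, in percentage points**

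| Difference in nun share | Gap 5 points | Gap 10 points | Gap 15 points |
|---|---|---|---|
| 0 points | 0 | 0 | 0 |
| 10 points | 0.5 | 1.0 | 1.5 |
| 20 points | 1.0 | 2.0 | 3.0 |
| 30 points | 1.5 | 3.0 | 4.5 |

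The sign reverses if nuns are concentrated in the shorter-service band.

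**Against sampling error.** With equal bands (assumed, 400/3 ≈ 133 each), the standard error of the worked difference is √[(0.545 × 0.455 + 0.590 × 0.410)/133] = √(0.4899/133) = 0.061, or 6.1 points. The 4.5 points are about three quarters of one standard error (4.5/6.1 = 0.74). That is modest, but unlike sampling error it does not shrink with a larger sample.

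**The case against.** **A stronger reading is tempting.** A reader might infer that the population and size of the main analysis contradict each other, because Hypothesis 1 speaks of monks while the sample contains nuns. The documents do not support that. The participants sentence in the Methods uses the word monks for all 400 subjects of both genders. The Methods set the years question among monks and nuns, and the analysis section imposes no gender restriction. There is one sample size and no second figure to conflict with it. The SAP also labels no analysis as main or primary. Hypothesis 2 has to name both genders because it compares them, so the contrast with Hypothesis 1 is weak evidence that nuns were dropped.

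A men-only test would cost precision. If monks were 25%, 50% or 75% of the 400 (assumed), N would be 100, 200 or 300. The 95% half-width for a prevalence of 50%, 1.96 × √(0.25/N), would be 9.8, 6.9 or 5.7 points, against 4.9 at 400. That loss belongs to an unlikely reading and is not a defect of the plan as it stands.

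**Against the gender point.** It is a question of model specification and would remain if Hypothesis 1 were reworded. Naming logistic regression does not rule out a gender term. With equal nun shares the bias is zero, and the 4.5 points rest wholly on assumed figures.

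All of this is fair, and it limits what can be claimed to a possible bias. It does not remove the gap. The analysis section leaves gender out although the research question includes it and the literature review says that it matters.

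**Conclusion.** The wording difference is real but minor; both genders is the likely intent. The point that deserves a change is that the Statistical Analysis section names no gender term for the pooled years analysis. Whether this biases the result depends on the gender mix of the bands, which is unknown until data are in. The bias is zero with equal shares and 4.5 points (crude odds ratio 1.20) under the assumed 30% against 60% share and 15-point gap. No figure stated in the SAP is shown to be wrong. The change is worth making because it removes this source of bias at almost no cost.

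**What to change.** 1. In Hypotheses item 1 and Purpose item 1, say monks and nuns, to match the Methods. If men only is in fact meant, define that set in the Methods and Statistical Analysis sections and give its expected size.
2. In Statistical Analysis, state that the logistic regression of MSD on years of ordination is fitted in all participants with gender as a covariate, and that gender-adjusted odds ratios with confidence intervals are reported beside the crude chi-square. The gender coefficient also bears on Hypothesis 2, for which that section names no test.
3. Tabulate gender by ordination band, so that a reader can see whether adjustment had anything to correct. Crude and adjusted odds ratios can differ slightly even when the bands are balanced.

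Results shown separately for monks and for nuns are optional and descriptive; no hypothesis asks whether the years association differs by gender.

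The cost is a few words in three sections, one model term and one small table. No new data are needed.

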## Purpose of the study

This study will be conducted to:

- 1- Survey the relationship between duration of years since ordination and musculoskeletal disorders among Egyptian monks.
- 2- Survey the relationship between musculoskeletal disorders and gender of monks and nuns.

## Significance of the study

The prevalence of musculoskeletal illnesses as a global cause of chronic pain and disability is predicted to rise in the future years. Worldwide, millions of people suffer from the illness known as chronic musculoskeletal pain. It can appear in many areas of the body, such as the back, knees, or shoulders, and be brought on by a variety of things, including ageing, vigorous exercise, bad posture, and trauma. (Chen, et al.,2023)

The world health organisation (WHO) estimates that one in three persons worldwide suffer from a musculoskeletal illness that is chronically painful. About 45 million workers in the European Union are affected by musculoskeletal disorder diseases, which are the most common and expensive work-related health issues. (Gorasso, et al.,2023)

The prevalence of MSD among Thai monks was discovered to be correlated with older age, longer ordination, and a BMI under 25 kg/m2. (Whaikit., et al 2020).

Monks' health in 2016, the fifth most common disease was osteoarthritis (AL, 2019). Monks had chronic diseases such as joint pain and arthritis (Pornprasert., et al 2016) when considering only low back pain It has a prevalence of 59.3 percent, similar to research in The previous monks who found back pain, waist pain, 53.8%, the prevalence of knee pain was 15.7% less than the previous research in monks. Osteoarthritis of the knee 32.5% (Suvithanpatthanabandit., et al., 2015), but in the direction Similarly, the factors related to MSD symptoms of monks as a whole were found that the factors related to MSD Discuss symptoms were age, years of ordination, and death.

the highest prevalence in the lower back (hundred 59.3 percent), followed by shoulders (25.0%), neck (22.5%), and knees (15.8%), respectively, when classified by the

severity of symptoms. past was found to affect daily routines day according to the practice of the monks 11.5 percent and causing them to stop performing their daily activities according to the practice of monks 6.5 percent. (Whaikit., et al 2020).

To our knowledge there is lack in the literature regarding MSD among monks and nuns in Egypt.

#### **Delimitations**

This study will be delimited to:

- 1- Sample size will be 400.
- 2- Age starts from 24 years old and more.
- 3- Body mass index (BMI) between 18.5 to 24.9 kg/m2
- 4- Years of ordination
  - (1-3) years "novice" or "probationary".
  - (4-10) years of monasticism.
  - more than 10 years of monasticism.
- 5- Samples will be selected from several monasteries in Egypt.
- 6- All data collected by Arabic version of Nordic questionnaire.

## **Basic assumptions**

Subjects will faithfully follow our instructions and answer the questionnaire during participation.

### **Definition of terms:**

Musculoskeletal Disorders (MSDs): are injuries or disorders that affect muscles, nerves, tendons, joints, cartilages, and the spinal discs, that are associated with exposure to risk factors at the work place (Antwi-Afari., et al., 2023)

A **Monk** or **Nun:** are those who practise religious asceticism through monastic living; this refers to celibate individuals who continuously resided in a monastery. (not married) and consumed meals prepared in the monastery. (**Avdeenko.,2019**)

Monastery: building in which monks live and worship. (Chuchalin., 2023).

Neck pain: defined as pain in the neck or the cervical region of the body. It is usually common in adults causing morbidity, disability and huge health cost (though not to the extent of LBP) (Boswell, Trescot, Datta et al., 2007; Côté, Van, Cassidy et al., 2008).

**Nordic questionnaire:** the extended Nordic musculoskeletal Q is a reliable instrument that measure the prevalence, severity and impact of musculoskeletal symptoms. (Rhee H, Miles ms, Halpern CT et al., 2005)

# **Chapter 2**

## **Review of literature**

This chapter will review the literatures about the following:

- 1- Anatomy of Human backbone
- 2- Low back pain
- 3- Neck Pain
- 4- Knee Pain
- 5- Risk factors associated MSDs
- 6- Pathways to developing MSDs
- 7- Association between Age and MSDs
- 8- Association between sex and MSDs
- 9- Association between Work demand and MSDs
- 10- Association between Years of ordination and MSDs

## **Anatomy of Human backbone**

The human backbone or the vertebral column is made up 33 important group of bones called vertebrae which protect the spine and provide stability to the body. The vertebrae at the neck region are known as the cervical vertebrae and they are made up of 7 vertebrae. The thoracic vertebrae follows the cervical vertebrae and they are made up of 12 vertebrae. The lumbar vertebrae which is made up of 5 vertebrae follows the thoracic vertebrae. The sacrum which is made up of 5 sacral vertebrae fused together also follows the lumbar vertebrae. The vertebral column ends with the coccyx which is made up of 4 coccygeal vertebrae fused together. Each vertebra is separated from the other by a disc which acts as a shock absorber and helps to make the vertebral column flexible. Each vertebra is connected to the other by a ligament. The backbone is surrounded by muscles, blood vessels and nerves. All these structures can be the source of pain. (klement et al , 2011)

#### Low back pain

is experience of an unpleasant sensation and emotional state that can potentially cause tissue damage. (elwood 2012). Pain is the human body's protective mechanism that prevent further damage to an injured part (s) (yam et al 2018). Low back pain also known as lumbo-sacral pain affects areas between the 12th rib and the gluteal folds (Waheed, 2003).

It can be grouped based on the duration of the signs and symptoms in to acute, sub-acute and chronic, lasting for 6 week or less, between 6 and 12 weeks, and over 12 weeks respectively. Low back pain can be localized (when it does not radiate into the lower limbs) or referred (when it radiates into the lower limb(s); known as sciatica).

Lower back pain is the most prevalent MSDs and a leading cause of disability amongst workers (**Picavet & Schouten, 2003**). It is also an essential cause of morbidity, early retirement due to ill health, absenteeism, and job changes (**Cunningham, Flynn, & Blake, 2006**).

Studies have reported on the prevalence of lower back pain amongst Thai monks.

For example, **(Whaikit., et al 2020)** reported that 59.3% of Thai monks who developed MSDs had LBP.

Prayer-based exercises effectively affect pain severity and endurance of flexor muscles in patients with non-chronic lower back pain. (Jokarborzabad., et al.,2021)

These studies have clearly shown that LBP is the number one MSDs experienced by monk irrespective of the country they find themselves.

## **Neck Pain**

Neck pain defined as pain in the neck or the cervical region of the body. It is usually common in adults causing morbidity, disability and huge health cost (though not to the extent of LBP) (Boswell, Trescot, Datta et al., 2007; Côté, Van, Cassidy et al., 2008). Lifetime prevalence has been found to be ranging from 26% to 71% with estimated 12 months prevalence of 30% to 50% (Boswell et al., 2007; Côté et al., 2008; Peloso et al., 2007).

Neck pain often arise from structures around the neck such as muscles, vertebral bones, facet joints, ligaments, and capsules etc. (Cagnie, Danneels, Tiggelen, et al., 2007).

Injury to soft tissues in the neck region and/or prolonged wear and tear are the main causes of neck pain. The pain may also be referred from the shoulders and upper back. It can rarely be caused by infection (eg. TB) or Cancers (Ariëns, Van, Bongers et al., 2000; Côté et al., 2008). Neck pain may be described as specific and non-specific. Specific when the cause can be identified and non-specific (or idiopathic) when it cannot be associated to any specific pathology. Only 10% of neck pains are specific, thus the cause of most neck pain cannot be linked to a specific pathology (Mayou & Farmer, 2002). Studies have reported on the prevalence of neck pain amongst Thai monks.

For example, (Whaikit., et al 2020) reported that (22.5%) of neck pain in Thai monks.

## Knee pain

Prostration From a standing to a kneeling position, the exercise is performed by placing the head down and hitting the ground with the forehead and flexing the elbows for a brief period of time. (Nazish., & Kalra., 2018). Some exercise is believed to be beneficial to the joint because it increases the circulation of synovial fluid, which bathes the articular cartilage with nutrients and maintains periarticular muscle strength.. Repetitive, high-intensity joint impact and torsional loading (twisting) also appear to be associated with joint degeneration. A series of studies that evaluated the longitudinal effects of aging and exercise on OA of the knee and hip after 5 and 8 years of follow-up found no increased risk of developing OA in exercisers, in this case runners, compared with age-similar controls. (Panush et al., 1995)

Previous studies have shown Prayer has no effect on knee and hip osteoarthritis, and may be related with hand osteoarthritis. (Yılmaz, et al., 2008). Thai Buddhist monk studies shown There was no significant association between the average daily lifetime kneeling in any positions and symptomatic radiographic knee osteoarthritis.

## (Tangtrakulwanich, et al 2006)

### Risk factors associated MSDs

Several risk factors have been linked to the development of MSDs in the work environment. These factors include biomechanical, physical, individual susceptibility

and psychosocial conditions (Barbe & Barr, 2006). Physical factors include doing high repetitive movement, maintaining awkward position while working, exposure to high level vibration, and stationary working posture, which elevate the physical loading of joints and surrounding soft tissues (including nerves, muscles, blood vessels) leading to injuries (Tantawy et al., 2017).

However, the intensity of the injuries depends on factors such as the frequency, intensity, and duration of the exposure (Bernard, 1997). Other physical risk factors such as, prolong sitting, static poor posture, working over the head, excessive work demands on the employee, and poor work control pattern, are associated with upper limb WRMSDs (Walker-Bone & Cooper, 2005).

Psychosocial risk factors have also been link to the occurrence of MSDs (Warren, 2010). These factors include distress, anxiety and depression (Magnavita, Elovainio, Nardis et al., 2011; Nahit, Hunt, Dunn, et al., 2003). Further, when it comes to individual susceptibility, body mass index (BMI) which an indicator of the body's adiposity plays an important role in the development of WRMSDs. Body mass index is body's weight divided by the height squared. People with higher BMI has been found to be more likely to develop MSDs compared to those with lower BMI (Viester, Verhagen, Hengel, et al., 2008). Also, high stress level has been found to increase body weight leading to an increase in BMI (Yang et al., 2014) and therefore is a risk factor for occurrence of WRMSDs.

